# 11.2 STUDY PRODUCT PACKAGING AND LABELING

The Ovaprene™ pouch will have a label on each side. Figure 1 below is an example of the single-panel label that will be affixed to one side of the Ovaprene™ pouch by the manufacturer. Sites will be provided with an additional single-panel lab to affix to the other side of the Ovaprene™ pouch; these site labels will include fields for Subject ID, Date Ovaprene™ is dispensed, and Date Ovaprene™ is removed from participant. Additional information will be included in the product instructions.

Version: 06.00 (FINAL) Date: June 13, 2019

Figure 1: Ovaprene™ Manufacturing Label

#### 11.3 DESCRIPTION AND PACKAGING OF CAYA DIAPHRAGM AND NONOXYNOL-9

The Caya® diaphragm is made of silicone rubber with a continuous, variable cross-section nylon polymer spring, encapsulated in the silicone rim. Its overall length is 75 mm and its overall width is 67 mm. The rim surrounds a contoured membrane with two cup-like structures and a flat area. The larger of the cups fits over the cervix and the smaller is intended to aid finger or thumb hooking of the rim for removal. The flat area provides contact with the vaginal wall.

The Caya diaphragm is manufactured by Wefo-Tec for Kessel Marketing & Vertriebs GmbH of Germany. Kessel Marketing is headquartered in Frankfurt, Germany, and is an ISO 13485 certificated company and producer of medical devices since 2005. Caya received FDA marketing clearance for the indication of pregnancy prevention in September 2014 and is distributed in the U.S. by HPSRx Enterprises, Inc., Salem, VA. Caya will be provided to study participants in its original commercial packaging showing the product's name, manufacturer, lot number, and expiration date.

Version: 06.00 (FINAL) Date: June 13, 2019

Gynol II® Vaginal Contraceptive Gel (Extra Strength, 3% N-9) is distributed by Revive Personal Products Company, Madison, NJ. It is a licensed, commercially available spermicide containing 3% nonoxynol-9 as the active ingredient. Inactive ingredients include lactic acid, methylparaben, providone, propylene glycol, purified water, sodium carboxymethylcellulose, sorbic acid and sorbitol solution. It is a clear, unscented, water-soluble, greaseless gel that should be stored at room temperature. Gynol II will be provided in its original commercial packaging showing the product's name, manufacturer, lot number, and expiration date.

### 11.4 STUDY PRODUCT STORAGE

All study products should be stored at room temperature as specified in the Study Procedures Manual.

#### 11.5 STUDY PRODUCT PREPARATION

The study products are ready to use and require no preparation.

#### 11.6 ADMINISTRATION

The participant will be instructed to insert Ovaprene™ at the end of menses, using a finger to push it into the vagina as far as it will comfortably go. She will check to make sure the device covers the cervix. Product use instructions will be provided.

The participant will be instructed to insert Caya with N-9 just before intercourse, following the package instructions, which will be provided. She will check to make sure the device covers the cervix.

#### 11.7 STUDY PRODUCT ACCOUNTABILITY

Dispensing of the Ovaprene™ device will be recorded on the device accountability log. The final return of the device, either by the participant or at the time of removal in the clinic, will be recorded on the accountability log. Additional instructions will be provided in the Study Procedures Manual.

A Caya diaphragm and a tube of Gynol II will be provided to the participant for the Caya PCT Cycle. Because these are marketed products, the participant will not be required to return them.

# 11.8 STUDY PRODUCT HANDLING AND DISPOSAL

All used and unused study product remaining at the end of the study will be recorded by the site and reconciled by the site monitor. After reconciliation, the Sponsor will provide instructions regarding disposal or return of product.

#### 12. ASSESSMENT OF SAFETY

#### 12.1 SAFETY PARAMETERS

#### 12.1.1 Adverse Events

As part of AE data collection, participant AEs will be assessed at each study visit; participant report of genitourinary and other symptoms will be documented and report of symptoms may result in follow-up laboratory assessments.

Version: 06.00 (FINAL) Date: June 13, 2019

Female participants will be asked to provide information on any AEs their male partners experience that are at least possibly related to product use, genitourinary in nature, or serious. Partner AEs meeting these criteria must be recorded on eCRFs.

#### 12.1.2 Physical Examination

A directed physical exam will be performed at each study visit if indicated, with changes on physical exam documented.

#### 12.1.3 Pelvic Exam

A pelvic exam will be performed at each study visit. Signs of irritation of the external genitalia, cervix, and vagina, as observed with the naked eye will be noted.

#### 12.1.4 Pregnancy Screen

A pregnancy test is required at Visit 1 on all participants. Note, however, that participants must be protected from pregnancy by prior female tubal sterilization in order to be eligible for study participation.

#### 13. ADVERSE AND SERIOUS ADVERSE EVENTS

# 13.1 DEFINITION OF ADVERSE EVENTS (AE)

An AE is any undesirable sign, symptom, or medical condition occurring after signing the ICF. Information about all AEs, whether volunteered by the subject, discovered by questioning, or detected through physical examination, laboratory testing, or other means, will be collected and recorded on the AE eCRF page and followed as appropriate.

Medical conditions present prior to study entry will be documented in the Medical History eCRF. However, medical conditions occurring after signing the ICF are to be recorded as AEs. Treatment-emergent AEs are defined as AEs with onset after the first dose of study drug or existing AEs that worsened after the first dose of study drug.

The Investigator is obliged to interview subjects at each clinic visit and clarify/discuss any abnormality that may indicate a potential AE.

Subjects should be encouraged to contact or visit the study site to report AEs that occur between scheduled visits.

AEs will be recorded from the time of signing the ICF until the end of the safety follow-up. If any AE is ongoing at the time of subject withdrawal, the subject will be asked to return for clinic visits or to respond to follow-up by telephone (if the AE is considered not related or unlikely related to study drug) until resolution or stabilization of this AE.

Any AE that occurs during the study must be monitored and followed up until one or more of the following criteria have been met:

- It has resolved to ≤ Grade 1 or baseline level
- Pathological laboratory findings have returned to normal
- Steady state has been achieved
- It has been shown to be unrelated to the study drug

Version: 06.00 (FINAL) Date: June 13, 2019

It is the responsibility of the Investigator to ensure that any necessary additional therapeutic measures and follow-up procedures are performed.

As far as possible, each AE will also be described by:

- Duration (start and end dates)
- Severity grade
- Relationship to the study drug
- Action(s) taken and, as relevant, the outcome

# 13.2 SERIOUS ADVERSE EVENT (SAE)

An AE is considered "serious" if, in the view of either the investigator or the sponsor, it:

- Results in death
- Is immediately life-threatening
- Requires in-patient hospitalization or prolongation of existing hospitalization
- Results in persistent or significant disability or incapacity
- Results in a congenital abnormality or birth defect
- Is an important medical event that may jeopardize the patient or may require medical or surgical intervention to prevent one of the outcomes listed above.

All participant and male partner SAEs, whether or not they are related to the study, must be recorded on eCRFs.

#### 13.3 UNEXPECTED ADVERSE EVENT

In previous studies of vaginal contraceptive devices, genital pruritus, genital irritation, genital pain, abnormal vaginal bleeding, symptomatic vaginal infections and UTIs, and Pap test changes were reported, thus making these expected AEs. An AE or suspected adverse reaction is considered "unexpected" if it is not listed above or in the product labeling for the Ovaprene™ or is not listed at the specificity or severity that has been observed. For example (not necessarily applicable to this study), under this definition, hepatic necrosis would be unexpected (by virtue of greater severity) if the labeling referred only to elevated hepatic enzymes or hepatitis. Similarly, cerebral thromboembolism and cerebral vasculitis would be unexpected (by virtue of greater specificity) if the labeling listed only cerebral vascular accidents. "Unexpected," as used in this definition, also refers to AEs or suspected adverse reactions that are mentioned in the labeling as occurring with a class of drugs or as anticipated from the pharmacological properties of the drug, but are not specifically mentioned as occurring with the particular drug under investigation.

#### 13.4 RELATIONSHIP TO STUDY PRODUCT

An Investigator who is qualified in medicine must make the determination of relationship to the investigational product(s) for each AE. The Investigator should decide whether, in his or her medical judgment, there is a reasonable possibility that the event may have been caused by the investigational product. For each AE, the assessment of relatedness should be made using the following scale:

Unrelated: Onset of the AE had no reasonable temporal relationship to administration of the study
product or a causal relationship to administration of the study product is biologically implausible or
the event is attributed to an alternative etiology.

Version: 06.00 (FINAL) Date: June 13, 2019

- Possibly Related: Onset of the AE has a reasonable temporal relationship to study product administration and a causal relationship is not biologically implausible.
- Probably Related: Onset of the AE has a strong temporal relationship to administration of the study
  product that cannot be explained by the participant's clinical state and a causal relationship is not
  biologically implausible.
- Definitely Related: Onset of the AE shows a distinct temporal relationship to administration of the study product that cannot be explained by the participant's clinical state or other factors or the AE occurs on rechallenge or the AE is a known reaction to the product or chemical group or can be predicted by the product's pharmacology.

If the relationship between the AE/SAE and the investigational product is determined to be "possible," "probable," or "definite" the event will be considered related to the investigational product for the purposes of expedited regulatory reporting.

#### 13.5 RECORDING AND GRADING ADVERSE EVENTS FOR SEVERITY

Adverse events spontaneously reported by the participant and/or in response to an open question from the study personnel or revealed by observation will be recorded during the study at the investigational site. The AE term should be reported in standard medical terminology when possible. All female adverse events and male adverse events that are assessed as at least possibly related to product use should be recorded on the AE eCRF. For each AE, the investigator will evaluate and report the date of onset, date of resolution, severity, causality, action taken, serious outcome (if applicable), and whether or not it caused the participant to discontinue the study. Each AE will be graded for severity using the March 2017 update of the Division of AIDS, National Institute of Allergy and Infectious Diseases (DAIDS) Table for Grading the Severity of Adverse Events, and the addenda for female and male genital AEs, which can be found at the following websites:

**Table 13 Guidance for Adverse Events** 

Adult and Pediatric AEs	https://rsc.tech-res.com/docs/default-source/safety/daids-ae-grading-table-mar2017.pdf
Female Genital AEs	http://rsc.tech-res.com/docs/default-source/safety/addendum_1_female_genital_grading_table_v1_nov_2007.pdf?sfv rsn=8
Male Genital AEs	http://rsc.tech-res.com/docs/default-source/safety/addendum_2_male_genital_grading_table_v1_nov_2007.pdf?sfvrs n=8

For clinical AEs NOT identified in the DAIDS AE Grading Tables, the following scale (as listed in the DAIDS Table for Grading the Severity of Adult and Pediatric AEs) should be used to grade severity:

- Mild: Mild symptoms causing no or minimal interference with usual social & functional activities with intervention not indicated
- Moderate: Moderate symptoms causing greater than minimal interference with usual social & functional activities with intervention indicated
- Severe: Severe symptoms causing inability to perform usual social & functional activities with intervention or hospitalization indicated
- Potentially Life-Threatening: Potentially life-threatening symptoms causing inability to perform basic self-care functions with intervention indicated to prevent permanent impairment, persistent disability, or death

Version: 06.00 (FINAL) Date: June 13, 2019

It is important to distinguish between serious and severe AEs. Severity is a measure of intensity whereas seriousness is defined by the criteria under **Section 13**. An AE of severe intensity may not be considered serious.

Participants are required to be protected from pregnancy by female tubal sterilization. Should a pregnancy occur, however, it must be reported as soon as possible to the Sponsor or designee and recorded on the pregnancy CRF. The participant will be discontinued from the study and appropriate exit procedures will be followed (Section 9.8). Note that pregnancy in itself is not regarded as an AE unless there is a suspicion that an investigational product may have interfered with the effectiveness of a contraceptive medication.

If the participant has been exposed to study product, the course of the pregnancy should be followed until it has an outcome (spontaneous miscarriage, elective termination, normal birth or congenital abnormality). If the participant seeks care outside the site, every effort should be made to obtain her consent for the site to receive a copy of her medical records related to the pregnancy, its outcome and the health of the neonate, if applicable.

Reports of congenital abnormalities/birth defects are SAEs. Spontaneous miscarriages should also be reported and handled as SAEs. Elective abortions without complications should not be reported as AEs.

#### 13.6 REPORTING SERIOUS ADVERSE EVENTS

All SAEs experienced by either a female participant or her partner, whether or not considered a suspected reaction, will be recorded from the time of signing the Informed Consent Form until 7 days following the end of treatment exposure.

Any SAE must be reported to the Sponsor or designee within 24 hours of discovery. If there is any question whether the event meets the criteria for "serious" it should be reported anyway. In addition, a completed Serious Adverse Event (SAE) Form must be faxed or emailed to the Sponsor or designee as soon as possible. The Investigator must complete, sign and date the SAE pages, verifying the accuracy of the information recorded on the SAE pages with the corresponding source documents

Additional follow-up information, if required or available, should all be faxed or emailed as instructed to the Sponsor or designee within one business day of receipt and this should be completed on a follow-up SAE form and placed with the original SAE information and kept with the appropriate section of the study file.

The Sponsor or designee will notify all participating investigators of potentially serious risks, from clinical trials or any other source, as soon as possible.

The Sponsor or designee will promptly investigate and follow up on all safety information it receives, with the cooperation of the investigator.

The investigator is responsible for complying with IRB requirements for AE reporting and the Sponsor or designee with copies of such correspondence.

# 14. STATISTICS

# 14.1 SAMPLE SIZE JUSTIFICATION

Approximately 45 participants will be enrolled, with the intent that approximately 25 will complete the study. Statistical considerations were not used to determine the size of the study population; rather, the study size was determined according to the maximum number of subjects that could feasibly be enrolled and complete this rigorous protocol in a reasonable time frame.

Version: 06.00 (FINAL) Date: June 13, 2019

#### **14.2 ANALYSIS PLAN**

All analyses will be conducted on an "as treated" basis; that is, product conditions are defined on the basis of treatment experienced and allocation errors are taken into account.

#### 14.2.1 Interim Analysis

An interim analysis will take place after at least 10 women have completed one Ovaprene® PCT cycle. The interim analysis is being performed to evaluate all primary endpoints as defined in Section 6 as well as to evaluate the proportion of Ovaprene® PCT cycles with an average of fewer than 5 progressively motile sperm per HPF in cervical mucus, across all women, in the presence of the Ovaprene® device.

#### 14.2.2 Sperm Penetration of Midcycle Cervical Mucus: Evaluation of Primary Objective

The primary method of evaluating changes in the PCT due to device use (primary objective) for each product condition will be the proportion of women and cycles (and 95% confidence interval [CI]) with an average (across 9 HPFs) of fewer than 5 PMS per HPF.

The mean, median, SD, and IQR of each woman's and cycle's average number (across 9 HPFs) of progressively motile sperm per HPF will be calculated separately for baseline and each test PCT. Qualitative assessments of change from baseline, if any, will be based on the median and IQR, because of expected non-normality of test cycle data. These descriptive statistics will be calculated by site and pooled across sites.

There will be no statistical comparison between Caya PCT cycle results and Ovaprene™ PCT cycle results. Caya PCT cycle results will be reviewed in the context of published Caya PCT studies; it is expected that Caya PCT results in this study will be similar to published Caya PCT results, which will give confidence to the Ovaprene™ PCT results in this study.

#### 14.2.3 Secondary Objective: Release of active component from device

The mean, median, SD, and IQR of ferrous gluconate values associated with fewer than 5 progressively motile sperm per HPF will be calculated across all women. The mean, median, SD, and IQR of ferrous gluconate values at each time point at which it is collected will also be calculated across all women. The mean, median, SD, and IQR of ferrous gluconate values in used devices will be calculated. The mean, median, SD, and IQR of cervical mucus and vaginal pH before and after sex in the absence of and the presence of the device will be calculated across all women.

#### 14.2.4 Secondary Objective: Safety

Tables and listings will be created for all treatment-emergent AEs (TEAEs), defined as those occurring on or after first product use. However, the primary evaluation of safety will be the subpopulation of safety AEs that are urogenital, product-related, and/or serious. Data will be presented according to relatedness of the finding to study product, whether AEs had onset before or after intercourse, by gender and by site, and pooled across sites separated by gender, and the severity/seriousness of the AE. There are no planned statistical tests for this objective.

Version: 06.00 (FINAL) Date: June 13, 2019

For other safety endpoints, baseline and comparison time points will be qualitatively compared as shown below:

**Table 14: Endpoint Evaluations** 

	Goal	Baseline	Compared with
Changes in CBC,* chemistries,* and ferritin, colposcopy*	Assess effect of device on these endpoints after one cycle of use in the absence of sex, compared with before insertion	OS1	OS5
Nugent score,* vaginal microflora, vaginal antibacterial	Assess effect of device on these endpoints over one cycle, in the absence of sex, compared with before insertion	OS1	OS2, OS3, OS4, OS5
activity, and soluble markers	Assess effect of device on these endpoints after the device has been in place for one cycle, with multiple acts of sex up until 72 hours before the last visit, compared with before insertion	OP1	OP5
Vaginal antibacterial activity and soluble markers of inflammation	Assess effect of device insertion on these markers, in the absence of sex	BP1	OS1 after device insertion Baseline sample cannot be collected before device insertion at this visit because collection technique (vaginal lavage) is likely to affect subsequent samples taken at this visit.
	Assess effect of device on these markers after sex, compared with after sex with no device in place	BP2	OP3
	Assess effect of device on these markers after sex, compared with before sex	OP1	OP3

\* Also done at Visit 1 to establish eligibility

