#### b) Visit CP2 – the PCT visit, 2-3 hours after intercourse and within 27 hours of the CMC:

The participant will return to the clinic 2-3 hours after coitus ends and within 27 hours of the mucus check visit.

- Diary review, AEs, medications, and indications for a directed physical exam, wet mount, and other tests will be managed as described for Visit 2 (BP1).
- The participant will undergo a pelvic exam:
  - o Signs of irritation of the external genitalia, cervix, and vagina, as observed with the naked eye, will be noted.
  - o Cervical mucus will be examined for midcycle characteristics and the presence of sperm (see **Appendix 2**).
  - o Vaginal sample(s) will be collected for the presence of sperm.
  - o The Caya will be removed.
  - o Caya PCT results will be managed as listed in **Appendix 3**.
- The participant will next undergo the Ovaprene™ safety cycle.
- Participants will be instructed as follows:
  - Call at the onset of her next menses to tentatively schedule Visit OS1 on the day following the end of menses. Adjustments to this visit will be made as needed.
  - o Sex with or without condoms is permitted after Visit CP2 until the first day of the next menses, after which the participant should abstain from intercourse and other vaginal activity.n

<sup>n "Other vaginal activity" includes insertion of vaginal medications/products other than the study product (prescription or over-the-counter), as well as insertion of sex toys, fingers, or anything else into the vagina. Tampons may be used during all days of menses in the Baseline PCT and Caya PCT cycles, but only during the first three days of menses in Ovaprene cycles.

Version: 06.00 (FINAL) Date: June 13, 2019

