# e) Visit OS5, 21-23 days after insertion (approximately cycle day 27-29, or sooner if menses is expected to begin):

- An acceptability questionnaire will be administered.
- Blood will be drawn for CBC, serum chemistries, and serum ferritin.
- The procedures described above for Visit OS2 will be completed, except that no OPK will be dispensed.
- Ovaprene™ will be removed and stored for later analysis.
- A colposcopic exam will be completed.
- Cervical mucus will be collected for ferrous gluconate and pH.
- The participant will next undergo an Ovaprene™ PCT cycle. She will be instructed to:
  - o Call at the onset of her next menses to tentatively schedule Visit OP1 on the day following the end of menses. Adjustments to this visit will be made as needed.
  - Use non-spermicidal, lubricated condoms (dispense as needed at this visit) from the first day of her next menses until day 10 of that cycle, and to abstain from intercourse and other vaginal activityr starting on Day 10 until after Visit OP2, the CMC visit.

<sup>q Assaying for ferrous gluconate in the cervical mucus is considered exploratory throughout the study.

"Other vaginal activity" includes insertion of vaginal medications/products other than the study product (prescription or over-the-counter), as well as insertion of sex toys, fingers, or anything else into the vagina. Tampons may be used during all days of menses in the Baseline PCT and Caya PCT cycles, but only during the first three days of menses in Ovaprene cycles.

Version: 06.00 (FINAL) Date: June 13, 2019

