# 9.5.1 Ovaprene™ PCT Cycle - Visits and Procedures:

#### a) Visit OP1, the day following the end of menses (approximately cycle day 6):

• Diary review, AEs, medications, and indications for a directed physical exam, wet mount, and other tests will be managed as described for Visit 2 (BP1).

Version: 06.00 (FINAL) Date: June 13, 2019

- The participant will be asked whether she used non-spermicidal, lubricated condoms
  from the onset of menses in this cycle. If instructions were not followed, she will be
  reinstructed. If she used a spermicide or spermicidal lubricated condom, Visit OP1 will
  be rescheduled in the next cycle. Otherwise, the visit may continue at the
  investigator's discretion.
- The participant will undergo a pelvic exam:
  - o Signs of irritation of the external genitalia, cervix, and vagina, as observed with the naked eye, will be noted.
  - o A colposcopic exam will be completed.
  - o Cervical mucus will be collected for pH and ferrous gluconate.
  - o Vaginal sample(s) will be collected for pH, ferrous gluconate, Nugent score, microflora, antibacterial activity, and soluble markers.
- The participant will insert Ovaprene™ using written instructions, with assistance if needed. The clinician will check the placement.
- An ovulation predictor kit (OPK) with instructions will be dispensed.
- The participant will be instructed as follows:
  - Begin daily urine testing on day 10 of that cycle (adjusted as needed to normal cycle length) and contact the study coordinator when the OPK test yields a "high" result. Visit OP2 (the mucus check visits) will then be scheduled for that day or the next day.
  - O Until day 10, she and her partner should use condoms for each act of intercourse. There should be no intercourse or other vaginal activity,s and her male partner should not have an ejaculation, starting on day 10 until after Visit OP3.

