#### d) Visit OP4, 24 hours after the PCT:

- Diary review, AEs, medications, and indications for a directed physical exam, wet mount, and other tests will be managed as described for Visit 2 (BP1).
- The participant will undergo a pelvic exam:
  - o Signs of irritation of the external genitalia, cervix, and vagina, as observed with the naked eye, will be noted.
  - o The position of the device relative to the cervix will be noted.
  - o Vaginal sample(s) will be collected for ferrous gluconate and pH.
- Participants will be instructed as follows:
  - o Intercourse is permitted after this visit for the rest of this cycle with the following restrictions:
    - Condoms lubricated with something other than nonxynol-9 must be used (dispense as needed).
    - No sex or other vaginal activitym is permitted in the 72 hours prior to the final visit in the cycle.
  - O A tentative appointment will be made for the next visit, taking into account the participant's usual cycle length and the need to have that visit take place before the participant's next menses begins but as late as possible in the cycle. The participant will be instructed to contact the site immediately if it appears that her menses is starting before the tentatively scheduled appointment.

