#### 3.7.6 Nugent's Score and Vaginal Microflora

Nugent's score (from central lab, if available; otherwise, use local lab) and antibacterial (anti-E. coli) activity in CVF, soluble markers of inflammation in CVF and changes in these endpoints from Visit OS1 to OS2 through OS5 and from Visit OP1 to OP5, will be summarized by 6-number statistics at each visit. Antibacterial and soluble marker changes will also be summaries for these changes: BP1 to OS1, BP2 to OP3 and OP1 to OP3. Vaginal microflora and staphylococcus aureus assessment on the ring will not be analyzed by HD and the vendor analysis of the data will be included as an appendix of the final clinical study report.

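### OP1 cannot serve as the 'before sex' comparator for OP3, and OP1-to-OP5 has a sex-free window at one end only

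*Protocol*

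**What the plan says.** Two rows of Protocol Table 14 (section 14.2.4) start from OP1.

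- **OP1 to OP5**, for Nugent score, microflora, antibacterial activity and soluble markers. The goal is the device's effect after a cycle in place, "with multiple acts of sex up until 72 hours before the last visit, compared with before insertion".
- **OP1 to OP3**, for antibacterial activity and soluble markers: "Assess effect of device on these markers after sex, compared with before sex".

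SAP 3.7.6 repeats both. Changes "from Visit OS1 to OS2 through OS5 and from Visit OP1 to OP5, will be summarized by 6-number statistics at each visit", and the antibacterial and soluble-marker changes are added for "BP1 to OS1, BP2 to OP3 and OP1 to OP3". The SAP leaves microflora to the vendor's own analysis.

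The intercourse instructions before these visits differ.

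- Before OS1 (Protocol 9.3.2 b): sex is allowed until the first day of menses, "after which the participant should abstain from intercourse and other vaginal activity".
- Before OP1 (Protocol 9.4.1 e, repeated in 9.5.1 e for the second PCT cycle): "Use non-spermicidal, lubricated condoms (dispense as needed at this visit) from the first day of her next menses until day 10 of that cycle". OP1 falls on about day 6, inside that period. At OP1 only spermicide use forces rescheduling; other departures are left to the investigator (9.5.1 a).
- Before OP5 (Protocol 9.5.1 d): no sex or other vaginal activity "is permitted in the 72 hours prior to the final visit in the cycle".

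OP3 takes place 2-3 hours after one act without a condom and with the device in place. At EVMS the OP3 marker sample is taken 6 hours after the PCT (9.5.1 c).

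**The concern.** A before/after contrast can be attributed to one factor only if the other factors stay fixed. The OP1-to-OP3 row is presented as after sex against before sex, yet OP1 has no device, falls in a different part of the cycle, and is not guaranteed to precede sex. A reader of the summary table could credit to intercourse a change that comes from the device or from the cycle, or the reverse.

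The OP1-to-OP5 row is the only one that covers a full cycle of wear with sex. It holds recent intercourse off at the end but not at the baseline. If recent condom intercourse moves a marker, the change from baseline carries that shift with the opposite sign.

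**Working it through.** The plan has no figure to reproduce: section 14.1 says the study size has no statistical basis, and these comparisons carry no tests.

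**Step 1. Line up the visits** (28-day examples in Protocol Tables 6, 9 and 11; visit text in 9.2 to 9.5).

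| Visit | Device | Cycle day | Intercourse before sampling |
|---|---|---|---|
| BP2 | none | 15 | one condomless act, 2-3 h before the visit |
| OS1 | not yet inserted (EVMS antibacterial and soluble-marker sample: 6 h after insertion) | 6 | none since day 1: (6 − 1) × 24 = 120 h |
| OS3 | in place 14 − 6 = 8 days | 14 | none since day 1 |
| OP1 | not yet inserted | 6 | condom intercourse allowed; required gap 0 h |
| OP3 | in place 15 − 6 = 9 days | 15 | one condomless act, 2-3 h before the visit |
| OP5 | in place 28 − 6 = 22 days | 28 | none for 72 h |

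At EVMS the BP2 and OP3 marker samples both come 6 h after the PCT, about 8-9 h after intercourse.

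**Step 2. What each contrast contains.** Let D be the device effect, C the cycle-phase effect, S the effect of the test act of intercourse, and R any effect of recent intercourse still present at OP1. Assume the effects add.

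- OP1 to OP3 = D + C + S − R. One difference, four unknowns.
- OS3 to OP3 ≈ S with the device in place. Days in place (8 and 9) and cycle day (14 and 15) nearly match.
- BP2 to OP3 ≈ D after sex. Cycle day and intercourse match.
- OS1 to OS5 = D + C without sex.
- OP1 to OP5 = D + C + any lasting effect of sex earlier in the cycle − R.

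OP2 would have been the natural in-cycle sample before sex with the device in place, but it does not collect these markers (9.5.1 b; Appendix 1). OS3 is the nearest substitute already collected.

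**Step 3. How far R could move OP1-to-OP5.** Let q be the share of women with recent intercourse before OP1, and s the resulting shift at OP1 in units of the SD of change. Neither is in the documents; both are assumptions.

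Bias = −(q × s). With n = 25 completers, the half-width of a 95% t interval is 2.064 / √25 = 0.41 SD. The interval is a yardstick only; the SAP plans none for these endpoints. The chances come from the noncentral t distribution.

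| q | s | Bias | Expected change if true effect is +0.5 | Chance that the 95% CI lies above 0 | Expected change if true effect is 0 |
|---|---|---|---|---|---|
| 0 | any | 0 | +0.50 | 0.67 | 0 |
| 0.25 | +0.5 | −0.125 | +0.375 | 0.44 | −0.125 |
| 0.5 | +0.5 | −0.25 | +0.25 | 0.22 | −0.25 |
| 0.5 | +1.0 | −0.50 | 0.00 | 0.025 | −0.50 |
| 0.25 | −0.5 | +0.125 | +0.625 | 0.85 | +0.125 |
| 0.5 | −0.5 | +0.25 | +0.75 | 0.95 | +0.25 |

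The sign of the bias follows the sign of s, which is unknown.

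**The case against.** The strongest reply is that the plan already holds better contrasts. OS1 to OS2-OS5 shows the device with abstinence throughout. BP2 to OP3 shows the device after sex, with cycle day, condomless intercourse and sampling time matched. Table 14 also labels the OP5 row as against before insertion, so there OP1 does what its label says. Intercourse is recorded in the eDiary (Protocol 10.3). The comparisons are descriptive, and the primary safety evaluation is adverse events (14.2.4). All of this stands. It confines the problem to two rows and lowers the stakes, but it does not make OP1 a before-sex sample taken with the device in place.

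OS3 is also imperfect. It comes from another cycle and another device, it is tied to the OPK high result only where possible (9.4.1 b), and it is not time-matched to the EVMS 6-hour OP3 sample. These limits stand and must be stated with the result.

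A reader might infer more than the documents support:

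- **That OP1-to-OP5 hides device-related inflammation.** This needs recent condom intercourse to be common before OP1 and to raise the markers. Neither is documented, and in the 28-day example most of the three days before OP1 fall within menses.
- **That colposcopy is affected.** Table 14 and SAP 3.7.4 compare colposcopy from OS1 to OS5, not from OP1.
- **That the plan itself treats recent sex as moving the markers.** No reason is given for the 72-hour rule. The abstinence before OS1 belongs to a cycle defined as having no intercourse. The tampon limit covers every Ovaprene cycle, so it applies before OP1 too.

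**Conclusion.** The point holds for two of the six Table 14 rows. OP1-to-OP3 cannot answer its stated goal, because device, cycle phase and intercourse change together; this follows from the visit schedule alone and needs no assumption about size. OP1-to-OP5 has a required sex-free interval of 72 hours at the end and 0 hours at the start, so recent intercourse can bias it. The 0 hours is the permitted minimum, not expected behaviour. Two OP1 visits in each of about 25 completers give about 50 baselines, and how many follow recent intercourse is unknown. On the assumed range in Step 3, a true change of +0.5 SD would appear as anything from 0 to +0.75 SD; the documents supply neither the size nor the direction. The consequence is misreading of a descriptive table, not a false test result, and the ability to see a device effect on these markers is not lost.

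**What to change.** 1. **Table 14, last row, and SAP 3.7.6.** Add OS3-to-OP3 as the before/after-sex contrast for antibacterial activity and soluble markers, reported beside OP1-to-OP3. Relabel OP1-to-OP3 as a comparison with before insertion, not as an effect of sex. State the limits of OS3: different cycle and device, OPK timing only if possible, and the EVMS OP3 sample at 6 hours.
2. **SAP 3.7.6, OP1-to-OP5.** Use eDiary intercourse dates to flag OP1 samples taken within 72 hours of intercourse, and report the change with and without them. SAP 3.1.2 currently plans only by-subject listings of diary data. The flag rests on self-report.
3. **Interpretation.** Name OS1-to-OS5 and BP2-to-OP3 as the main device contrasts. For antibacterial activity and soluble markers, limit OS1-to-OS5 to non-EVMS sites, because EVMS takes that OS1 sample 6 hours after insertion. Note that OS1-to-OS5 still spans about day 6 to day 28, whereas BP2-to-OP3 matches cycle day.
4. **Protocol 9.4.1 e, 9.5.1 a, 9.5.1 d and 9.5.1 e.** Reconcile the differing intercourse instructions before OP1 and OP5, or state why they differ.

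The cost of items 1 to 3 is one added summary, one derived flag and some relabelling, with no new samples and no added burden on participants. The analysis does not depend on a new pre-visit rule. The protocol version is dated June 13, 2019 and the synopsis estimates last completion on September 1, 2019. On those dates a new rule would reach few cycles and would mix two kinds of OP1 baseline.
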